While supracervical hysterectomy and concomitant SCP are associated with lower rates of mesh exposure,¹⁰⁻¹² potential negative consequences of a supracervical hysterectomy include morcellation of unanticipated uterine malignancy,¹³ cervical stump prolapse/elongation, cyclic vaginal bleeding, and reduced anterior vaginal support (Myers EM, [name] et al., in press). When conducting a supracervical hysterectomy, power morcellators are the most common method used to extract the amputated uterine corpus. The potential risks of power morcellation were recently highlighted by the FDA safety notification which focused on the potential to disseminate fragments of an undiagnosed uterine leiomyosarcoma throughout the abdomen, which negatively impacts prognosis (<http://www.fda.gov/MedicalDevices/Safety/AlertsandNotices/ucm393576.htm>). With these

recent developments the focus has shifted towards performing total hysterectomy for delivery of an intact specimen through the vagina.

Vaginal mesh exposure has been a problematic complication with both abdominal SCP and minimally invasive SCP. Widely disparate rates of mesh exposure ranging from 0%¹⁴ to 27%¹⁵ have been reported. A systematic review of ASCP outcomes in 2004 reported an overall rate of 3.4%,⁶ and a recent meta-analysis of robotic-assisted SCP reported an overall rate of 2%.¹⁶ Some consistent risk factors for mesh exposure are non-Type 1 polypropylene mesh (knitted, small-pore mesh materials) and smoking.^{17,18} Some studies have identified total hysterectomy as a significant risk factor. In an evaluation of patients enrolled in the CARE trial, 6% had evidence of mesh exposure at 2 years, with concomitant hysterectomy presenting almost a 5-fold increased risk.¹⁸ The rate at 6 years rose to 10.5%.⁵ More than 50% of subjects in this trial, however, had a non-Type 1 polypropylene mesh. Akyol et al. demonstrated a 2-fold increased risk (12%)¹⁹ and Bensinger et al. a 7-fold increased risk (8.2%)²⁰ of concomitant total hysterectomy. In contrast, 4 retrospective studies in which Type 1 polypropylene mesh was used revealed no increased risk of mesh erosion with concomitant total hysterectomy.^{14,21-23} These widely discrepant rates of mesh exposure may be related to surgical technique, graft material and/or suture materials used for mesh attachment.

Rationale for need to study suture material for mesh attachment during SCP

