Data will be entered by study staff at each site into a REDCap database that will be stored on a secure server by the Data Coordinating Center. Study data will be monitored by the Data Coordinating Center as outlined below under Study Monitoring and Documentation. All collected data must be entered into REDCap within 5 business days. Any queries to data entered into REDCap will be addressed by site staff within 5 business days. It is each site's responsibility to regularly check REDCap for data queries. See REDCap Data Entry Protocol for instructions on data entry and query resolution.

Each site will maintain all essential study documents in original format and source documentation that support the data collected on study participants in compliance with ICH/GCP guidelines. Documents must be retained until at least 2 years have elapsed since the formal discontinuation of the clinical investigation. Each site will take measures to ensure that these essential documents are not accidentally damaged or destroyed.

OUTCOME MEASURES

Primary Outcome Measure

The primary outcome of this trial is the incidence of vaginal mesh and suture exposure rates related to the SCP mesh for both arms of the study through 1-year after surgery. Any suture or mesh visible in the vagina that is not at the position of a midurethral sling will be considered a positive outcome. Some participants may also undergo vaginal placement of a mesh sling for stress incontinence in a more distal vaginal location. Exposure of this mesh will not be considered a positive outcome for the primary outcome.

Secondary Outcome Measures

Secondary outcomes that we will measure include a composite of objective and subjective measures, self-reported outcomes, and assessment of complications as outlined below:

1. Assessment of efficacy at 1 year of each type of suture material using the composite cure as outlined below in a-d. Participants will be considered a surgical success for this composite outcome if each of the following four criteria are met:
 - a) Anatomic success: Leading edge of the prolapse is at or above the hymen (POP-Q point Ba and Bp \leq 0) and the vaginal apex descends less than 1/3 of the total vaginal length (C $<$ - TVL/3)
 - b) Subjective success: Patient denies symptoms of vaginal bulging per PFDI-20 question 3, answering "No" or "Yes" but "Not at All" bothersome (< 2)

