The rate of reported mesh exposure varies greatly from 0-27%, as discussed in our Background section on page 2 of the Investigator Protocol. Based on published data both at our institution and elsewhere in the literature, we determined that a 10% and 1% rate of mesh exposure in the two groups is both supported by data and clinically relevant, thus we are estimating a 9% difference in mesh erosion rates between the two groups: 1% vs 10%. This is a clinically significant difference that would affect a change in clinical practice.

Sample Size

The power calculation was performed using the statistical computation software Epi Info™ 7.1.3.10, developed on 3/11/14. It is a trademark of the Centers for Disease Control and Prevention and uses chi square for its computation of sample size for studies based on categorical data comparison such as the current study.

We are planning a study of independent cases and controls with 1 control(s) per case. Prior data indicate that the mesh exposure rate among controls is 10%. If the mesh exposure rate for experimental subjects is 1%, we will need to study 80 experimental subjects and 80 control subjects to be able to reject the null hypothesis that the failure rates for experimental and control subjects are equal with probability (power) 0.8. The Type I error probability associated with the test of this null hypothesis is 0.1. The alpha of 0.1 is based on a one-sided hypothesis, estimating that mesh exposure rates will be higher in the study arm using permanent suture compared to the study arm using absorbable suture. We will use an uncorrected chi-squared statistic to evaluate this null hypothesis. We plan to enroll a total 200 subjects across sites to account for up to 20% loss to follow up, thus the use of chi square is appropriate given the adequately large sample size.

We feel the sample size is appropriate based on our sample size calculation, taking into account the estimated rates of mesh exposure in the two groups, as well as our clinical judgment of the number of procedures that are performed each year at the study sites. In the past year each

study site has performed 50 cases, for a total of 200 cases at all combined sites. Therefore our sample size of 100 subjects per study arm is feasible for completion in the time allotted.

Primary Hypothesis

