Site staff must not make any changes or deviate from this protocol, except to protect the life and physical well-being of a subject in an emergency. Site staff shall notify the PI and the reviewing IRB of any deviation from the investigational plan to protect the life or physical well-being of a subject in an emergency, and those deviations which affect the scientific integrity of the clinical investigation. Such notice shall be given as soon as possible, but no later than 5 working days after the emergency occurred, or per prevailing local requirements, if sooner than 5 working days. All deviations from the investigational plan, with the reason for the deviation and the date of occurrence, must be documented and reported to the Data Coordinating Center. Study sites may also be required to report deviations to their IRB per local guidelines and government regulations.

Data Safety Monitoring Board

A data safety monitoring board (DSMB) comprised of 2 external physicians ([name] and [name]) will review all adverse events (AEs) that occur across sites. A semi-annual report of all AEs will be generated and sent to the DSMB every 6 months.

All Serious Adverse Events (SAEs) will be reported to the study DSMB via email within 2 business days of site staff being informed of its occurrence. The PI and study coordinator will be cc'd on all communications between study sites and the DSMB. Copies of de-identified source documentation regarding the SAE will be included in the email, as well as a copy of the Adverse Event Form. Source documentation may include the operative/clinic note, Investigator/surgeon correspondence regarding the SAE, the original CRF, or other meaningful clinical information. Any request for additional documentation to determine relatedness to the operative procedures or pelvic floor will be honored within 5 business days.

Study PI: [contact]

Project Manager: [contact]

DSMB: [name], [contact]

DSMB: [name], [contact]

The PI ([name]) will be responsible for ensuring that all sites comply with DSMB requests. The DSMB will then provide a written evaluation of each SAE detailing a judgment as to whether or not the event was deemed to be study related and a judgment as to whether, based on the review of the event, the study can:

1. Continue unchanged
2. Continue with recommended changes
3. Be stopped

The DSMB, PI, and each site will keep copies of all relevant information and committee decisions.

Criteria for Study Termination

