After 50% of all study subjects have presented for the 6-week post-operative check, the overall rate of mesh and suture exposure will be calculated. If this rate is >12%, the study will be terminated. A second stopping parameter will be a difference in erosion rates between the two groups of >50%.

Reporting Adverse Events

Adverse events will be recorded and reported according to criteria and timeline below. Sites will also follow local regulatory standards for AE reporting.

All AEs must be recorded on the AE CRF, entered into the site AE log, then entered into REDCap. An event number will be assigned by each site and recorded on the CRF according to the number of AEs reported per patient. Each site investigator will determine the relationship of the AE to the operative procedures, the relationship of the AE to the pelvic floor, and the severity of each reportable AE.

SAEs must be reported to the DSMB within two business days as outlined above in the Data Safety Monitoring Board section.

Reportable AEs include those determined to be related to the operative procedures or pelvic floor. AEs not related to the operative procedures or pelvic floor will not be collected. Operative procedures include the following: Hysterectomy, sacrocolpopexy, sling, anterior and posterior vaginal repairs.

Please note that underlying diseases are not reportable AEs unless there is an increase in severity or frequency during the course of the investigation. Death should not be recorded as an AE, but as an outcome of a specific SAE. If an AE has not resolved at the time of AE Form completion, save form as incomplete in REDCap until resolved. Once resolved, complete item 22 on AE form and enter into REDCap and save form as complete.

Adverse Event Definitions

Adverse Event: any untoward medical occurrence, unintended disease or injury, or any untoward clinical signs (including abnormal laboratory finding) in subjects, whether or not related to the operative procedures

Serious Adverse Event: an adverse event that:

- Led to death
- Led to serious deterioration in the health of the subject that either resulted in
 - a life-threatening illness or injury
 - a permanent impairment of a body structure or a body function
 - in-subject or prolonged hospitalization of existing hospitalization
 - medical or surgical intervention to prevent life-threatening illness or injury or permanent impairment to a body structure or a body function

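### The 12% overall exposure limit is checked once, at a point tied to the 6-week visit, for a 1-year outcome; the plan does not say which exposures count, what time point 12% refers to, or whether the check is repeated

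*Combined protocol and SAP*

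**What the plan says.** **The rule.** Criteria for Study Termination sets the time of the calculation: "After 50% of all study subjects have presented for the 6-week post-operative check, the overall rate of mesh and suture exposure will be calculated". It then gives the limit: "If this rate is >12%, the study will be terminated". No later or repeated calculation is described. The section does not say whether exposures found after the Week 6 visit in early participants enter the rate.

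**The second parameter.** The same section adds: "A second stopping parameter will be a difference in erosion rates between the two groups of >50" (per cent). It gives no time for this comparison and does not say whether the difference is absolute or relative.

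**The outcome.** Primary Outcome Measure defines "the incidence of vaginal mesh and suture exposure rates related to the SCP mesh for both arms of the study through 1-year after surgery". Follow-Up Visits and Table 1 schedule a vaginal examination at Week 6 and at Year 1. The only scheduled contact between them is the Month 6 telephone call.

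**The planning figures.** Statistical Methods has the authors "estimating a 9% difference in mesh erosion rates between the two groups: 1% vs 10" (per cent). Sample Size says: "We plan to enroll a total 200 subjects across sites to account for up to 20% loss to follow up".

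**Other oversight.** Data Safety Monitoring Board says: "A semi-annual report of all AEs will be generated and sent to the DSMB every 6 months". No exposure rate is attached to that report. The board's stated choice to continue, change or stop follows its review of each serious adverse event.

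**The concern.** Every woman receives the same mesh, and Choice of mesh material says that nothing is yet known of how it performs in sacrocolpopexy. The overall rate is the plan's only numeric rule that responds to exposure common to both arms. It is calculated once, at a moment defined by the 6-week visit, while the outcome takes a year to complete. Its limit is higher than the 1-year rate planned for the worse arm.

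If a material share of exposures is first seen after Week 6, an excess in both arms could pass this look and then meet no stated threshold, even if enrolment is still open. The wording also leaves the DSMB unable to tell which count to compare with 12%.

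**Working it through.** **Inputs.** Total enrolment 200, planned 1-year rates 10% and 1%, and 20% loss come from Statistical Methods and Sample Size. The 12% limit and the 50% trigger come from Criteria for Study Termination. The share *f* of 1-year exposures visible by 6 weeks is not in the documents; I assume 50%, 75% and 100%.

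**1. Women at the look.** The plan needs 80 per arm, and 160 / 0.8 = 200. Half of 200 is 100, about 50 per arm. (The uncorrected chi-square formula returns 79 per arm at one-sided alpha 0.05 and 57 at the stated one-sided 0.10. This does not affect the present point, which rests on the 200.) The plan states no operating characteristic for the 12% rule, so there is no figure of its own to reproduce.

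**2. Trigger.** 12 / 100 is not above 12%, so stopping needs 13 or more exposures. The planned pooled rate is (10% + 1%) / 2 = 5.5%.

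**3. Chance of stopping.** P(X₁ + X₂ ≥ 13), with X₁ ~ Binomial(50, f·p₁) and X₂ ~ Binomial(50, f·p₂), exact:

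| 1-year rates (permanent vs absorbable) | f = 50% | f = 75% | f = 100% |
|---|---|---|---|
| 20% vs 20% | 20% | 75% | 97% |
| 20% vs 10% | 4% | 33% | 76% |
| 20% vs 1% | 0.2% | 4% | 24% |
| 10% vs 1% (plan) | <0.01% | 0.02% | 0.27% |

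**4. Pooling.** In the third row the average is (20% + 1%) / 2 = 10.5%, below 12%. Complete 1-year data would still stop the trial only 24% of the time.

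**5. Sensitivity.** If the trigger were 80 women (stop at 10 or more), 20% vs 1% gives 0.7%, 9% and 32%. If the rate counts everything known at the look, 20% vs 1% at f = 50% gives 0.2% to 2.9% with detection at visits only, and 0.5% to 10% with continuous detection, for enrolment lasting 6 to 36 months.

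**6. Repeating the calculation.** Assume even enrolment, f = 50%, the rest found at Year 1, all known findings counted, semi-annual looks after the first until enrolment ends, and a crossing treated as a stop. With 20% in both arms, the expected cumulative rate at the last look is:

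- 12-month enrolment, month 12: 200 × 10.5/12 = 175 women seen at Week 6, essentially none at Year 1; rate 10%.
- 18-month enrolment, month 18: 200 × 16.5/18 ≈ 183 seen, 200 × 6/18 ≈ 67 at Year 1; (67 × 0.20 + 116 × 0.10) / 183 = 13.7%.
- 24-month enrolment, month 24: 200 × 22.5/24 ≈ 188 seen, 100 at Year 1; (100 × 0.20 + 88 × 0.10) / 188 = 15.3%.

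By simulation, the chance of stopping rises from 20% to 26%, from 21% to 74%, and from 32% to 91%. These shift by a few points with the exact timing of visits. The 24-month starting value exceeds 20% because about 12.5 women already have Year 1 findings at the first look: (12.5 × 0.20 + 87.5 × 0.10) / 100 = 11.25%. At 20% vs 1% with 24-month enrolment, the chance rises only from 0.2% (first look on Week 6 findings alone) to 3.7%.

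**7. Unneeded stops.** At the planned 10% vs 1%, with every 1-year exposure already visible, the formula in step 3 gives 0.27% at 100 women. It reaches 0.54% at 108, where 13 still triggers because 13/108 = 12.04%, and is below 0.01% at 200 (25 or more). With fewer women it is larger: at a pooled 5.5%, 4.6% with 25, 1.9% with 50 and 0.8% with 75.

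**The case against.** **Enrolment may be over before later findings arrive.** Sample Size counts 200 cases in the past year. At that pace all surgery is done by about month 12, just as Year 1 visits open (month 11 with the window). This stands, and limits the gain at that pace. It also rules out a tempting stronger reading: that no woman has had a Year 1 examination at the look, and that later women are still being operated on when many Year 1 findings come in. The first holds with fast enrolment, the second needs slow enrolment. Fast enrolment would require nearly every case to enrol, and the protocol itself expects some eligible women to decline.

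**The documents do not show how much exposure appears between Week 6 and Year 1.** In the cited trial "6% had evidence of mesh exposure at 2 years, with concomitant hysterectomy presenting almost a 5-fold increased risk", rising to 10.5% at 6 years, but that lies beyond this trial's horizon and over half of those women had a different type of mesh. The 8% at 1 year from the investigators' own series is a single time point. This stands: a reader might infer that the look precedes most exposures, and the documents do not support that. Hence the range for *f*.

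**Other safeguards exist.** Related exposures are reportable adverse events, the DSMB sees all adverse events every 6 months, and serious ones reach it within 2 business days. Read as a relative difference, the second parameter is met at 20% vs 1%. So it would be wrong to say that exposure is never looked at again. But the adverse event review has no exposure threshold, the second parameter has no look time or scale, and a between-arm difference cannot detect exposure shared by both arms.

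**Conclusion.** The point holds as a gap in definition and repetition. A single pooled look is timed by the 6-week check, the outcome runs to 1 year, and neither the exposures that count nor the meaning of 12% is stated.

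A reader might go further and infer that the rule almost never acts. The documents do not support that: with 20% in both arms it acts between 20% and 97% of the time over the assumed range of *f*. The very low figures belong to 20% vs 1% with a low *f*, and pooling is the main limit there. Later looks do not cure that case.

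The value of repeating the calculation depends on the length of enrolment, which the documents do not fix. For 20% in both arms and *f* = 50%, it is small at about 12 months and large at 18 to 24 months. All figures assume equal arms and 100 women at the first look.

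**What to change.** The sponsor and DSMB should reconcile the 6-week look with the 1-year outcome in Criteria for Study Termination. They should state which exposures count at the look (Week 6 findings only, or everything known by then) and whether 12% is a 6-week or a 1-year rate.

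From the existing 50% look until enrolment ends, each semi-annual DSMB report should also show the cumulative overall exposure rate from all findings to date: Week 6, Month 6 call, unscheduled and Year 1. It should give the number of women who have reached each time point and set the rate against the sponsor's own limit. Starting at the 50% look keeps the denominator at about 100 or more and avoids the larger false-stop chances seen with fewer women. No new limit is proposed.

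The cost is protocol wording, one table in a report that already exists, and the small chance of an unneeded stop in step 7. This is a harm rule, so the added looks do not inflate the error rate of the primary comparison.

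### The protocol contradicts itself on whether serious adverse events that a site judges unrelated, including fatal ones, are recorded and reach the DSMB

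*Combined protocol and SAP*

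**What the plan says.** The Data Safety Monitoring Board section sets a remit with no relatedness condition. The DSMB "will review all adverse events (AEs) that occur across sites". For serious events, "All Serious Adverse Events (SAEs) will be reported to the study DSMB via email within 2 business days of site staff being informed". The email must carry de-identified source documents "as well as a copy of the Adverse Event Form". The DSMB then gives a written evaluation of each SAE. That evaluation includes "a judgment as to whether or not the event was deemed to be study related" and an opinion on whether the study may continue unchanged, continue with changes, or stop.

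Reporting Adverse Events starts in the same direction: every AE is to be entered on the CRF, the site log and REDCap, and SAEs are to go to the DSMB within two business days. It also assigns the determination of relatedness to the site investigator, describes reportable AEs as those found to be related, and states that "AEs not related to the operative procedures or pelvic floor will not be collected". On fatal events it says "Death should not be recorded as an AE, but as an outcome of a specific SAE".

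Adverse Event Definitions makes an AE independent of its relation to the operative procedures, and defines an SAE as an AE meeting certain seriousness criteria.

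**The concern.** The DSMB is meant to give an independent view of causality and, from it, a view on whether the trial should go on. If the site's view of causality decides whether the event is recorded at all, the DSMB can agree with a site's finding of relatedness or overrule it, but it can never overturn a finding of no relation, because it does not see the event. That is the error an independent board is best placed to catch.

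The suture is allocated in the operating room, and the protocol describes no blinding of the investigator who judges relatedness. Five sites work from this text, so they may also handle the same kind of event differently.

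**Working it through.** The point is about consistency of wording. It depends on no error rate, effect size or sample size, so there is no figure to reproduce. The check is to set the provisions side by side and follow one event through them.

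1. **Does the non-collection sentence reach SAEs?** Yes, on its words. It applies to AEs, and Adverse Event Definitions makes an SAE a subset of AEs. No sentence in either section exempts SAEs.

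2. **Does it reach deaths?** Yes, by the same route. A death is entered only as the outcome of an SAE. If that SAE is not collected, the AE record has no entry to which the death can be attached.

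3. **Which provisions point the other way?** Five do: the DSMB's review of all AEs; the DSMB section's rule on all SAEs; the SAE sentence in Reporting Adverse Events; that section's instruction to record all AEs; and the AE definition, which disregards relatedness. The conflict is thus partly between the two sections and partly inside Reporting Adverse Events.

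4. **Can both rules be followed at once?** Take an SAE that the site judges unrelated to the procedures and to the pelvic floor. The DSMB section requires an email enclosing the AE Form. The non-collection sentence means that no AE Form is completed. A site cannot comply with both.

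5. **Who decides relatedness?** The site investigator decides under Reporting Adverse Events, and the DSMB decides for each SAE under its own section. The DSMB may also ask for supporting material: "Any request for additional documentation to determine relatedness to the operative procedures or pelvic floor will be honored within 5 business days". Two layers of judgement can coexist, but only if the first does not determine which events reach the second.

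6. **How wide is the filter?** It is narrower than the word unrelated suggests. The event must be unrelated on both scales. Under Relationship of AE to Operative Procedures, an event with a timely relation to surgery and a plausible alternative cause is still possibly related. Under Relationship to Pelvic Floor, an event with no other reasonable explanation counts as related. Perioperative SAEs would seldom be excluded. Later events in the one-year follow-up are more exposed, because unrelated to the procedures is defined by the absence of evidence of a timing relationship, and the site applies that test alone.

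7. **Is there another route to the DSMB?** None is stated. The End of Study Form records reasons for withdrawal, and sites follow local reporting standards, but neither is directed to the DSMB. The Data Coordinating Center verifies roughly 25% of each site's data and checks compliance. A site that had left out an unrelated SAE could cite the non-collection sentence as compliance.

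**The case against.** The strongest reply is that specific rules govern general ones. Two SAE-specific sentences, one in each section, require reporting without any relatedness condition, against one general sentence about AEs. On that reading every SAE reaches the DSMB, and the non-collection sentence concerns only non-serious events. This is at least as natural a reading as the other. It shows that loss of SAEs is possible rather than certain, but it does not remove the conflict: the protocol never states which rule takes precedence, and the exclusion is unqualified.

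Three stronger inferences should be resisted.

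- A reader might conclude that site judgement does remove SAEs and deaths from the DSMB's view. The documents support only that it can, at a site that follows the exclusion.
- A reader might conclude that a death judged unrelated is recorded nowhere. The End of Study Form, the coordinating center's check on efforts to trace lost participants, and local reporting might each capture it. What is established is that the AE record need not contain it and that none of these is a stated route to the DSMB.
- A reader might conclude that the AE comparison in Secondary Hypothesis 3 is distorted by the exclusion. Secondary Outcome Measures defines the adverse outcome as events related to the procedure or the pelvic floor, so leaving out unrelated events is part of the endpoint. Collecting unrelated SAEs would not change that comparison.

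**Conclusion.** The contradiction stands and should be corrected. As written, an SAE that the site judges unrelated to both the procedures and the pelvic floor, including a fatal one, must be sent to the DSMB under one set of sentences and need not be recorded under another. Where a site follows the second, the DSMB cannot review or reverse the site's judgement.

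No number of affected events can be given. The documents state neither an SAE rate nor the share of SAEs that sites would call unrelated. If every site follows the SAE-specific sentences, the number is zero. If some follow the exclusion, it is limited by the broad definitions of relatedness. The conclusion rests on the wording alone, and assumes that no separate instruction to sites settles which sentence prevails.

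**What to change.** Reconcile the two sections with a short amendment.

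- In Reporting Adverse Events, state that all SAEs, including those leading to death, are recorded on the AE CRF and sent to the DSMB within the existing time limit, whatever the site's relatedness judgement.
- Limit the non-collection exemption to non-serious AEs unrelated to the procedures and to the pelvic floor.
- Align the sentence on recording all AEs, and the DSMB section's wording on reviewing all AEs, with that exemption, so that both refer to the events actually collected.

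No new rule is needed to document the DSMB's opinion, since a written evaluation of each SAE and retention of copies are already required. The cost is the amendment and a few more SAE forms. It needs no added visits and no change to the definition or analysis of the secondary adverse-event outcome.
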